7 STATISTICAL METHODS & DETERMINATION OF SAMPLE SIZE

7.1 Statistical and Analytical Plans

Complete and specific details of the statistical analysis will be described and fully documented in the SAP. The statistical analyses will be performed using SAS (SAS Institute Inc., Cary, North Carolina, USA) under the UNIX operation system.

An interim efficacy analysis will be performed when Stage 1 subjects have completed the Week 24 disease assessments in R/R T-PLL subjects.

The primary efficacy analysis will be performed for Stage 1 and Stage 2 subjects after their completion of the Week 24 disease assessments in R/R T-PLL subjects.

The final analysis will be performed when all subjects have discontinued the study or have completed protocol defined follow-up time, whichever is later.

7.2 Determination of Sample Size

Approximately 37 subjects will be enrolled based on the optimal adaptive 2-stage design.¹² The adaptive 2-stage design is presented in the [Table 6](#) below and details will be provided in the SAP.

Table 6. Sample Size Using Optimal Adaptive 2-Stage Design

H₀: p ≤ 20% versus H₁: p ≥ 40% 1-β = 80%, 1-sided test, significance level = 0.05				Comments
n₁ = 14				
S	n₂(S)	n(S)	r(S)	
≤ 3	0	14	0	Stop for futility after Stage 1
4	23	37	11	R/R versus treatment-naïve Stage 2 sample size distribution will vary depending on the number of responses from Stage 1
5	20	34	10	
6	20	34	10	
≥ 7 ^a	17	31	9	

CR = complete remission; CRi = CR with incomplete bone marrow recovery; PR = partial response; R/R = relapsed or refractory
p: probability of achieving a response (CR, CRi, or PR).

Power: 1-β = 80%.

Significance level: 10% (2-sided).

n₁: Sample size for Stage 1.

S: Number of responses from Stage 1.

n₂(S): R/R sample size for Stage 2.

n(S): Total R/R sample size of Stage 1 and Stage 2.

r(S): Critical value of total number of responses from Stage 1 and Stage 2 to demonstrate efficacy. "Critical value" is the threshold beyond which the null hypothesis is rejected (i.e., claiming efficacy). For example, the test is statistically significant if the number of responders is at least 12 with a sample size of 37 subjects.

a. The Stage 2 portion will still be conducted to evaluate efficacy in additional subjects even if the Stage 1 portion shows significant efficacy.

7.3 Definition for Analysis Populations

The Full Analysis Set (FAS) includes all R/R T-PLL subjects who received at least 1 dose of study drug. The FAS will be used for all safety, pharmacokinetic, efficacy and baseline analyses. The analyses for the treatment-naïve subjects will be included in the SAP.

7.4 Statistical Analyses for Efficacy

The primary efficacy endpoint will be the ORR, defined as the proportion of subjects achieving CR, CRi, or PR as their best overall response in R/R T-PLL subjects as per investigator based on the T-PLL consensus criteria 2019.¹¹ The best overall response of CR/CRi/PR will be defined as achieving CR, CRi, and PR at any point during the study (CR/CRi will need confirmation assessment based on the T-PLL consensus criteria 2019).¹¹ The estimate and 90% confidence interval for ORR based on binomial distribution will be constructed. Subjects who have not achieved any component of ORR will be considered as nonresponders in the calculation of ORR at the time of analysis.

The secondary efficacy analysis will be based on the following endpoints: PFS, duration of response, time-to-progression, event-free survival, disease control rate, overall survival, and number of eligible subjects reaching autologous or allogeneic transplantation. All secondary endpoints will be assessed per investigator assessment in R/R T-PLL subjects based on the T-PLL consensus criteria 2019.¹¹

Time-to-event endpoints will be analyzed using Kaplan-Meier methodology. Median time-to-event and the corresponding 95% CI will be provided. Binary endpoints will be analyzed using binomial distribution and estimate of proportion along with 95% confidence interval will be provided.

Details on the primary and other efficacy analyses are provided in the SAP.

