Preliminary clinical response from 1 subject treated with venetoclax in combination with ibrutinib was recently reported at the 23rd Congress of the European Hematology Association;⁸ clinical response was demonstrated by significant clinical improvement, significant decrease in spleen size, and improvement in disease-related laboratory values such as leukocytosis, lactate dehydrogenase, and β 2 microglobulin (B2M).

Clinical Hypothesis

The combination of venetoclax with ibrutinib can be safely administered and will result in a greater percentage of subjects who achieve a best ORR (complete remission [CR]/CR with incomplete bone marrow recovery [CRi] + partial response [PR]).

In subjects with R/R T-PLL, the treatment with venetoclax plus ibrutinib will be considered promising if the combination yields a best ORR of 40% or greater. A poor rate is defined a best ORR of 20% or less based on the previously available data.

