5.6 Follow-Up for Subject Withdrawal from Study

To minimize missing data for efficacy and safety assessments, subjects who prematurely discontinue study drug treatment should continue to be followed for all regularly scheduled visits unless subjects have decided to discontinue the study participation entirely (withdrawal of informed consent). Subjects should be advised on the continued scientific importance of their data even if they discontinue treatment with study drug early.

If a subject prematurely discontinues study participation (withdrawal of informed consent), the procedures outlined for the final visit should be completed as soon as possible, preferably within 2 weeks. In addition, if subject is willing, a 30-day follow-up phone call after the last dose of study drug may be completed to ensure all treatment-emergent AEs/serious adverse events (SAEs) have been resolved.

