3.11 Post-Treatment Follow-Up and Survival Visits

Subjects who discontinue study drug but have not experienced progressive disease (PD) will return for post-treatment follow-up visits. The post-treatment follow-up visits will follow the same schedule as the visit schedule (i.e., Week 4, Week 8, Week 12, Week 16, Week 24, Week 36, and every 12 weeks thereafter). Subjects will return for post-treatment follow-up visits until study completion starting from study drug discontinuation until documented PD or other post-treatment therapies (including stem cell transplantation) are received. Follow-up hematology and disease response assessment data will be collected.

Survival information (i.e., the date and cause of death) will be collected via telephone calls at 6-month intervals or as needed to allow for more frequent survival analyses.

All subjects will be followed for survival information (i.e., date and cause of death, all poststudy anticancer treatment including stem cell transplantation, reasons for poststudy anticancer treatment, regimens, dates of initiation and completion, etc.) unless the subject requests to be withdrawn from the

study survival follow-up; this request must be documented in the subject's medical record and signed by the investigator. If the subject withdraws from study follow-up, the study staff may use a public information source (such as county records) to obtain information about survival status only, as appropriate per local regulations.

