3.14 Disease Assessment

All measurable disease must be documented at screening (baseline) before the first dose of study drug for all subjects based on the analysis of clinical laboratory tests (hematology), physical examination, and contrast-enhanced CT scan of involved neck, chest, abdomen, and pelvis (or MRI, if CT scan is medically contraindicated).

For all subjects, clinical response (laboratory and physical examination assessments) will be assessed by the investigator during Weeks 4, 8, 12, 16, 24, 36 and every 12 weeks thereafter, and at the final visit. Note: disease assessments may be performed approximately 7 days before the scheduled visit. The clinical response will be assessed by laboratory tests and physical examination (or ultrasound) using the T-PLL consensus criteria¹ (as outlined in [Table 2](#)).

If clinical response is suggestive of a CR/CRi, a CT scan with contrast (or MRI) should be done for a confirmatory assessment as outlined in [Section 3.13](#).

If a CT scan indicates a CR/CRi, a bone marrow aspirate and biopsy will be required as soon as possible to confirm the clinical response. For subjects who opt-in for correlative biomarker analyses, a portion of the bone marrow aspirate should be split for the optional biomarker collections listed in [Section 3.17](#).

To meet the CR criteria, the CT scan and bone marrow are both required to be negative. Some subjects fulfill all the criteria for a CR but have a persistent anemia, thrombocytopenia, or neutropenia apparently unrelated to T-PLL, but related to drug toxicity. These subjects will be assessed with a response of CRi.

Disease assessment will continue to be performed after the last dose of study drug until disease progression for any subject who has not experienced PD at the time of permanent discontinuation of venetoclax and ibrutinib.

Table 2. Clinical Response Criteria (Based on Physical Examination/Ultrasound and Laboratory Tests)

Group	Parameter	Complete Remission (all met)	Partial Remission (≥ 2 in Group A and ≥ 1 in B met)	Stable Disease (all met)	Progressive Disease (≥ 1 in Group A or B met)
A	Lymph nodes by physical examination/ultrasound	All long-axis diameters to < 1.0 cm	Decrease $\geq 30\%$ in SLD	Change of -29% to $+20\%$ in SLD	Increase in $> 20\%$ in SLD from Nadir ^a

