4.4 Sample Size Justification

Approximately 37 subjects with T-PLL will be enrolled based on the optimal adaptive 2-stage design. In Stage 1, 14 subjects with R/R T-PLL will be enrolled and the number of responders in Stage 1 will be used to determine the number of subjects to be enrolled for Stage 2.

Sample size calculation is done based on clinical hypothesis (using optimal adaptive 2-Stage design considering 1-sided significance level of 0.05 and power of 80%): In subjects with R/R T-PLL, the treatment with venetoclax plus ibrutinib will be considered promising if the combination yields a best ORR of 40% or greater, which is the alternative hypothesis. A poor rate is defined as best ORR of 20% or less, which is the null hypothesis.

The details of the design are presented in the [Table 1](#) below:

Table 1. Sample Size Using Optimal Adaptive 2-Stage Design

H₀: p ≤ 20% versus H₁: p ≥ 40%				Comments
1-β = 80%, 1-sided test, significance level = 0.05				
n₁ = 14				
S	n₂(S)	n(S)	r(S)	
≤ 3	0	14	0	Stop for futility after Stage 1
4	23	37	11	R/R versus treatment-naïve Stage 2 sample size distribution will vary depending on the number of responses from Stage 1
5	20	34	10	
6	20	34	10	
≥ 7 ^a	17	31	9	

n₁: Sample size for Stage 1.

S: Number of responses from Stage 1.

n₂(S): Sample size for Stage 2.

n(S): Total sample size of Stage 1 and Stage 2.

r(S): Critical value of total number of responses from Stage 1 and Stage 2 to demonstrate efficacy.

- a. The Stage 2 portion will still be conducted to evaluate efficacy in additional subjects even if the Stage 1 portion shows significant efficacy.

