6.2 Primary Efficacy Analysis

Overall Response Rate (ORR) (CR + CRi + PR) will be defined as the proportion of subjects who achieved best response of confirmed complete remission (CR), confirmed complete remission with incomplete marrow recovery (CRi), or partial remission (PR) based on the clinical response criteria proposed by the international T-PLL study group as assessed by investigator up through the Week 24 disease assessment (including early study termination). The corresponding 95% confidence interval for the proportion using Binomial distribution will be constructed. Subjects who have not achieved any component of ORR will be considered as nonresponders in the calculation of ORR at the time of analysis. An interim efficacy analysis will be performed when 14 subjects in Stage 1 have completed the Week 24 disease assessments. The final primary efficacy analysis will be performed for Stage 1 and Stage 2 subjects after their completion of at least Week 24 disease assessments.

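### The responder rule for the primary ORR does not stop at progression or new anti-T-PLL therapy, and the follow-up passages conflict on whether later responses would be recorded

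*Protocol*

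**What the plan says.** **Which responses count.** Protocol 7.4: "The best overall response of CR/CRi/PR will be defined as achieving CR, CRi, and PR at any point during the study". SAP 6.2 counts the best response "as assessed by investigator up through the Week 24 disease assessment (including early study termination"). Both treat a subject as a nonresponder only if no component of ORR was ever achieved. Protocol 3.2 adds no further limit.

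**What is collected after study drug stops.** Four passages apply:

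- Protocol 5.6: "subjects who prematurely discontinue study drug treatment should continue to be followed for all regularly scheduled visits", unless the subject withdraws consent.
- Operations Manual 3.14 (Protocol Appendix I): "Disease assessment will continue to be performed after the last dose of study drug until disease progression", for subjects without progression when both drugs are stopped.
- Operations Manual 3.11: post-treatment visits run "until documented PD or other post-treatment therapies (including stem cell transplantation) are received".
- Operations Manual 2.2 sets the same end of visits as 3.11, and a footnote to the biomarker sampling table (Operations Manual 3.17) repeats it.

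**How other endpoints treat new therapy.** SAP 6.3 censors PFS and TTP at the last assessment before non-protocol T-PLL therapy, and does not treat transplant in eligible CR subjects as such therapy. It counts new anti-T-PLL therapy as an EFS event. SAP 6.2 has no corresponding rule for ORR.

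**The concern.** Read literally, both responder definitions would credit venetoclax plus ibrutinib with a response first seen under another treatment.

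A hypothetical case: an R/R subject stops both drugs for toxicity at Week 8 without a response, completes the 30-day visit, starts another agent at about Week 13, stays on scheduled visits under Protocol 5.6, and meets the PR criteria at Week 24. This subject is a responder under Protocol 7.4 and SAP 6.2, yet PFS is censored before the new agent began. The PR thresholds are absolute values or reductions, mostly stated from baseline, so nothing in them screens the case out.

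Such responses can only raise the ORR, which is the one formally tested endpoint of a single-arm, investigator-assessed trial. The Stage 1 responder count S also decides the futility stop, the Stage 2 size and the critical value. One response separates S = 3 (stop) from S = 4 (continue), and 11 of 37 (not significant) from 12 of 37 (significant). Disease control rate also rests on best overall response, so it has the same gap.

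**Working it through.** **Inputs.** From Protocol Table 6 and SAP Table 1: n1 = 14, stop if S ≤ 3; (n2, r) = (23, 11) for S = 4, (20, 10) for S = 5 or 6, (17, 9) for S ≥ 7. The Table 6 footnote sets rejection at more than r responses in total (at least 12 of 37). Null rate: "A poor rate is defined a best ORR of 20% or less based on the previously available data". Alternative: the treatment "will be considered promising if the combination yields a best ORR of 40% or greater". Error rates: "1-sided significance level of 0.05 and power of 80" percent.

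**Formula.** P(reject) = Σ over S = 4 to 14 of P(Bin(14, p) = S) × P(Bin(n2(S), p) ≥ r(S) + 1 − S).

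**Step 1: reproduce the design.** At p = 0.20:

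| S | P(S) | P(reject given S) | Product |
|---|---|---|---|
| 4 | 0.1720 | 0.0715 | 0.0123 |
| 5 | 0.0860 | 0.1958 | 0.0168 |
| 6 | 0.0322 | 0.3704 | 0.0119 |
| ≥ 7 | 0.0116 | (summed over S) | 0.0085 |

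The unrounded sum is 0.0496. At p = 0.40 the same sum is 0.8003. Both stated figures reproduce, with almost no slack in the type I error. The chance of passing Stage 1, P(S ≥ 4), is 0.302 at 20%.

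**Step 2: let later-therapy responses count.** Assume a true study-drug ORR of 20%. Let f be the share of nonresponders who switch while still under response assessment; the documents give no value for f. Let switchers respond at 20%, the rate Protocol 2.1 gives for non-alemtuzumab therapy in pretreated patients. Then

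counted ORR = 0.20 + 0.80 × f × 0.20 = 0.20 + 0.16f.

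| f (assumed) | Counted ORR | P(S ≥ 4) | False-positive rate |
|---|---|---|---|
| 0 | 20.0% | 0.302 | 0.050 |
| 10% | 21.6% | 0.358 | 0.079 |
| 15% | 22.4% | 0.386 | 0.098 |
| 25% | 24.0% | 0.443 | 0.143 |

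In 37 subjects, f = 10% means 37 × 0.80 × 0.10 ≈ 3 switchers and 3 × 0.20 ≈ 0.6 expected counted responses.

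**Step 3: one response.** At p = 0.20, P(S = 3) = 0.250. Adding exactly one later-therapy response in Stage 1 lifts P(S ≥ 4) to 0.302 + 0.250 = 0.552 and the false-positive rate to 0.116.

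**Step 4: can such a response be recorded?**

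| Passage | Stops at progression? | Stops at new therapy? |
|---|---|---|
| Protocol 5.6 | No stop named | No stop named |
| Operations Manual 3.14 | Yes | No stop named |
| Operations Manual 2.2 and 3.11 | Yes | Yes |

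Protocol 5.5 lists progression, or a need for other antineoplastic agents, as a reason a subject may be withdrawn from the study and/or study drug. Leaving the study is therefore not compulsory. Under 5.6 a response after progression or a switch could be recorded. Under 3.14 this holds only for a switch without progression, and under 2.2 and 3.11 for neither.

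**The case against.** **The specific follow-up rules already end response visits at a switch.** Operations Manual 2.2 and 3.11 address post-treatment visits directly. Subjects who leave those visits move to six-monthly telephone contact for survival and new therapies, and the survival column of Appendix G contains no response assessment. Protocol 5.6 is a general sentence about limiting missing data. A reader might infer that the protocol requires response assessment after a switch. It does not: neither 5.6 nor 3.14 mentions switching, and 3.14 ends at progression. This objection stands as to likely size. It does not close the gap, because 2.2 and 3.11 govern visits rather than which responses count, and 5.6 remains in conflict with them.

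**The figures rest on assumptions.** This stands. No switching share is given, and 20% is the most Protocol 2.1 expects in R/R patients, applied here to subjects who have also stopped or failed study drug. Under SAP 6.2 the switch, the response and the visit must all fall by Week 24, and the 30-day visit is placed before any new therapy. The table is a sensitivity range; reading 0.079 to 0.143 as the trial's actual type I error would be wrong.

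**Other evidence and other rules exist.** ORR is not the only efficacy evidence, since PFS, DoR, TTP, EFS, disease control rate and OS are planned. Nor does SAP 6.3 exclude all later data: DoR has no new-therapy censoring and EFS counts new therapy as an event. The Statistical Programming Plan and the full consensus criteria are not available here, so absence of a rule is shown only for the protocol and SAP.

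**Transplant.** Protocol-directed transplant after CR is not a route for this bias, because those subjects are already responders.

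**Conclusion.** The gap is real and should be fixed, but it is not shown to be large. Both documents define the primary responder without an end at progression or new anti-T-PLL therapy, and applied as written they would count a response to later therapy in the ORR, in S and in disease control rate. Whether such responses reach the database depends on which conflicting follow-up passage a site follows. If Operations Manual 2.2 and 3.11 are followed throughout, the effect is near zero. If Protocol 5.6 is followed, the effect is upward only and of unknown size. The illustrated range assumes a true ORR of 20%, 10% to 25% of nonresponders switching under continued assessment, and a 20% response rate after the switch.

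The documents do not support the stronger conclusion that the trial's error control has failed. With 14 subjects in Stage 1 and a design error rate of 0.0496, however, one such response can change a decision. This warrants a should-fix rating.

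**What to change.** In Protocol 7.4 and SAP 6.2, state that only assessments on or before the earlier of investigator-documented disease progression and the start of non-protocol anti-T-PLL therapy count toward best overall response, and that subjects without a response by then are nonresponders. Use the SAP 6.3 meaning of non-protocol therapy, so that protocol-directed transplant after CR is not a cut-off. Apply the same rule to S at the interim analysis and to disease control rate, which the SAP does not currently list. List later assessments separately.

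Reconcile Protocol 5.6 and Operations Manual 3.14 with Operations Manual 2.2 and 3.11, so that sites have one rule for response visits after progression or new therapy. The counting rule protects the ORR whichever way that is settled. While editing, align the two response windows (any point during the study versus through Week 24); the SAP refers to the May 2019 protocol.

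The cost is a short text change in each document and a filter on dates that PFS and EFS already need. The ORR may be slightly lower. In particular, a later response on study drug would be lost if an earlier change had been recorded as progression: one Group B criterion suffices for progression, such as a neutrophil fall of at least 50%, and Protocol 6.2 notes that venetoclax may cause neutropenia. Listing the excluded responses would make any such loss visible.

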7.5 Statistical Analyses for Safety

The safety and tolerability will be assessed by evaluation of study drug exposure, AEs, SAEs, and deaths as well as changes in laboratory measurements, physical examinations, and vital sign parameters.

Statistical analyses for safety are described and fully documented in the SAP.

7.6 Interim Analysis

An interim analysis for efficacy and safety will be conducted after all subjects enrolled in Stage 1 have completed the Week 24 disease assessment for the purpose of submission. The study will stop for futility if the numbers of responses at Stage 1 is ≤ 3 .

Details pertaining to the interim analyses can be found in the SAP.

A Steering Committee composed of a group of investigators who are participating in this study and who are experts in the management of T-PLL and an internal specialist in infectious diseases who is not currently involved in the conduct or oversight of Study M18-803 will review efficacy, safety, and exploratory research throughout the study.

8 ETHICS

8.1 Independent Ethics Committee/Institutional Review Board

The protocol, informed consent form(s), recruitment materials, and all subject materials will be submitted to the IEC/IRB for review and approval. Approval of both the protocol and the informed consent form(s) must be obtained before any subject is enrolled. Any amendment to the protocol will require review and approval by the IEC/IRB before the changes are implemented to the study. In addition, all changes to the consent form(s) will be IEC/IRB approved.

8.2 Ethical Conduct of the Study

The study will be conducted in accordance with the protocol, Operations Manual, International Council for Harmonisation (ICH) guidelines, applicable regulations, and guidelines governing clinical study

conduct and the ethical principles that have their origin in the Declaration of Helsinki. Responsibilities of the investigator are specified in [Appendix B](#).

In the event a significant disaster/crisis (e.g., epidemic/pandemic, natural disaster, conflict/combat) occurs leading to difficulties in performing protocol-specified procedures, AbbVie may engage with study site personnel in efforts to ensure the safety of subjects, maintain protocol compliance, and minimize risks to the integrity of the study while trying to best manage subject continuity of care. This may include alternative methods for assessments (e.g., phone contacts or virtual site visits), alternative locations for data collection (e.g., use of a local laboratory instead of a central laboratory), and shipping investigational product and/or supplies direct to subjects to ensure continuity of treatment where allowed. In all cases, these alternative measures must be allowed by local regulations and permitted by IRB/IEC. Investigators should notify AbbVie if any urgent safety measures are taken to protect the subjects against any immediate hazard.

